## 15.12. Pharmacokinetic Endpoints

Concentration data in both blood serum and in cerebrospinal fluid will be assessed descriptively over time. Correlation with efficacy and safety outcomes may be performed, as the data warrant.

## 16. QUALITY CONTROL AND QUALITY ASSURANCE

During study conduct, the sponsor or its agent will conduct periodic monitoring visits to ensure that the protocol and good clinical practices (GCPs) are being followed. The monitors will review source documents to confirm that the data recorded on eCRFs are accurate. The investigator and institution will allow the sponsor monitors or its agents and appropriate regulatory authorities direct access to source documents to perform this verification.

The study site may be subject to review by IRB/IEC, and/or to quality assurance audits performed by the sponsor, or companies working with or on behalf of the sponsor, and/or to inspection by appropriate regulatory authorities.

It is important that the investigator(s) and their relevant personnel are available during the monitoring visits and possible audits or inspections and that sufficient time is devoted to the process.

## **17. ETHICS**

# 17.1. Institutional Review Board (IRB)/Independent Ethics Committee (IEC)

It is the responsibility of the investigator to have prospective approval of the study protocol, protocol amendments, ICFs, and other relevant documents, eg, subject instructions, recruitment advertisements, if applicable, from the IRB/IEC. All correspondence with the IRB/IEC should be retained in the Investigator Site File. Copies of IRB/IEC approvals should be forwarded to the sponsor.

The only circumstance in which an amendment may be initiated prior to IRB/IEC approval is where the change is necessary to eliminate apparent immediate hazards to the subjects. In that event, the investigator must notify the IRB/IEC and the sponsor in writing immediately after the implementation.

## 17.2. Ethical Conduct of the Study

The study will be conducted in accordance with the Declaration of Helsinki on Ethical Principles for Medical Research Involving Human Subjects, adopted by the General Assembly of the World Medical Association (2008).

In addition, the study will be conducted in accordance with the protocol, the International Conference on Harmonisation (ICH) guideline on Good Clinical Practice (GCP), and applicable local regulatory requirements and laws.

## 17.3. Subject Information and Consent

All parties will ensure protection of subject personal data and will not include subject names on any sponsor forms, reports, publications, or in any other disclosures, except where required by laws. In case of data transfer, the sponsor will maintain high standards of confidentiality and protection of subject personal data.

The ICF must be in compliance with ICH GCP, local regulatory requirements, and legal requirements.

The ICF used in this study, and any changes made during the course of the study, must be prospectively approved by both the IRB/IEC and the sponsor before use.

The investigator must ensure that each study subject, or his/her legally acceptable representative, is fully informed about the nature and objectives of the study and possible risks associated with participation. The investigator, or a person designated by the investigator, will obtain written informed consent from each subject or the subject's legally acceptable representative before any study-specific activity is performed. The investigator will retain the original of each subject's signed ICF and a copy provided to each subject.

# 17.4. Reporting of Safety Issues and Serious Breaches of the Protocol or ICH GCP

In the event of any prohibition or restriction imposed (ie, clinical hold) by an applicable Competent Authority in any area of the World, or if the investigator is aware of any new information that might influence the evaluation of the benefits and risks of the investigational product, the sponsor should be informed immediately.

In addition, the investigator will inform the sponsor immediately of any urgent safety measures taken by the investigator to protect the study subjects against any immediate hazard, and of any serious breaches of this protocol or of ICH GCP that the investigator becomes aware of.

## **18. DATA HANDLING AND RECORDKEEPING**

## **18.1.** Case Report Forms

As used in this protocol, the term eCRF should be understood to refer to either a paper form or an electronic data record or both, depending on the data collection method used in this study.

An eCRF is required and should be completed for each included subject. The completed original eCRFs are the sole property of the sponsor and should not be made available in any form to third parties, except for authorized representatives of the sponsor or appropriate regulatory authorities, without written permission from the sponsor.

The investigator has ultimate responsibility for the accuracy, authenticity, and timely collection and reporting of all clinical, safety, laboratory data entered on the eCRFs and any other data collection forms. The eCRFs must be signed by the investigator to attest that the data contained on the eCRFs is true. Any corrections to entries made on the eCRFs must be dated, initialed, and explained (if necessary) and should not obscure the original entry.

In most cases, the source documents are the hospital's or the physician's subject chart. In these cases, data collected on the eCRFs must match the data in those charts.

In some cases, the eCRF, or part of the eCRF, may also serve as source documents. In these cases, a document should be available at the investigator's site as well as at the sponsor and clearly identify those data that will be recorded on the eCRF, and for which the eCRF will stand as the source document.

## **18.2.** Record Retention

To enable evaluations and/or audits from regulatory authorities or the sponsor, the investigator agrees to keep records, including the identity of all participating subjects (sufficient information to link records, eg, eCRFs and hospital records), all original signed ICFs, copies of all eCRFs, SAE forms, source documents, and detailed records of treatment disposition, and adequate documentation of relevant correspondence (eg, letters, meeting minutes, telephone calls reports). The records should be retained by the investigator according to ICH, local regulations, or as specified in the Clinical Study Agreement, whichever is longer.

If the investigator becomes unable for any reason to continue to retain study records for the required period (eg, retirement, relocation), the sponsor should be prospectively notified. The study records must be transferred to a designee acceptable to the sponsor, such as another investigator, another institution, or to the sponsor. The investigator must obtain the sponsor's written permission before disposing of any records, even if retention requirements have been met.

## **19. PUBLICATION POLICY**

Publication of study results is discussed in the Clinical Study Agreement.

## **19.1.** Publications by Investigators

All information concerning the product, as well as any matter concerning the operation of the sponsor or its delegate, such as clinical indications for the drug, its formula, methods of manufacture, and other scientific data relating to it, that have been provided by the sponsor or its delegate and are unpublished, are confidential and must remain the sole property of the sponsor or its delegate. The Investigator will agree to use the information only for the purposes of carrying out this study and for no other purpose unless prior written permission from the sponsor or its delegate is obtained. The sponsor has full ownership of the eCRFs completed as part of the study.

All publications and presentations of the results of the Study are governed by the applicable provisions of the Clinical Trial Agreement between the sponsor (or its delegate) and the institution. By signing the study protocol, the investigator agrees that the results of the study may be used for the purposes of national and international registration, publication, and information for medical and pharmaceutical professionals by the sponsor or its delegate. If necessary, the authorities will be notified of the Investigator's name, address, qualifications, and extent of involvement. The Investigator may not publish or present any information on this study without the express written approval of the sponsor or its delegate. Additionally, the sponsor or its delegate may, for any reason, withhold approval for publication or presentation. Such manuscript or materials should be provided for sponsor/delegate review only after the final database, is available.

DSMB	Data and safety monitoring board
ECG	Electrocardiogram
eCRF	Electronic case report form
ET	Early termination
FAS	Full analysis set population
FDA	Food and drug administration
GRASSP	Graded redefined assessment of strength sensation and prehension
HR	Heart rate
ICH	International Conference on Harmonization
ISAFSCI	International standards to document remaining autonomic function after
	spinal cord injury
ISNCSCI	International standards for neurological classification of SCI
LEMS	Lower extremity motor score
LS	Least squares
MAR	Missing at random
MAS	Modified Ashworth scale
MedDRA	Medical dictionary for regulatory activities
mITT	Modified Intent to Treat
MMRM	Mixed-effects model for repeated measures
MNAR	Missing not at random
msec	Millisecond
MTD	Maximum tolerated dose
NCA	Non-compartmental approach
Neuro-QOL	Quality of life in neurological disorders

Statistical Analysis Plan

Sponsor	Name: F	ReNe	tX Bio,	Inc
Sponsor	Protocol	ID:	RNX-AX	<204-101

Abbreviation	Term
NLI	Neurological level of injury
PA	Prehension ability
PCS	Potentially clinically significant
PGIC	Patient Global Impression of Change
PK	Pharmacokinetics
PP	Prehension performance
PPS	Per Protocol Set
PT	Preferred term
QoL	Quality of life
QTcF	QT interval using Fridericia correction formula
ROM	Range of motion
SAE	Serious Adverse Event
SCI	Spinal cord injury
SCIM III	Version III of the spinal cord independence measure
SD	Standard deviation
SF-36	Short form - 36 v2 health survey
SF-6D	Short form six-dimension
SF-6D_R2	Short form six-dimension release 2
SOC	System organ class
TEAE	Treatment-emergent adverse event
TOEP	Toeplitz
TOEPH	Toeplitz with heterogeneity
TFLs	Tables, figures and listings
UEMS	Upper extremity motor score
WHO	World health organization
ZPP	Zone of Partial Preservation

1. Source Documents

The Statistical Analysis Plan was written based on the following documentation:

Document	Date	Version
Protocol	01Oct2020	V4.0
eCRF	21JAN2021	V3.0

2. Protocol Details

2.1 Study Objectives

Study RNX-AX204-101 is a two-part (Parts 1 and 2) study that will be run sequentially. Each part has unique objectives. The start of Part 2 will also be contingent on Data and Safety Monitoring Board (DSMB) review of data from Part 1.

2.1.1 Part 1 Single Ascending Dose

2.1.1.1 Primary Objective

To evaluate the safety, tolerability, and pharmacokinetics (PK) of ascending, single intrathecal lumbar slow bolus infusions of AXER-204 in subjects with chronic spinal cord injury (CSCI).

2.1.2 Part 2 Placebo-Controlled Repeat Dose

2.1.2.1 Primary Objective

- To evaluate the safety and tolerability of repeat intrathecal lumbar slow bolus infusions of AXER-204 compared to placebo in subjects with CSCI.
- To evaluate the PK of repeat doses of AXER-204 in subjects with CSCI.

2.1.2.2 Secondary Objectives

- To assess the efficacy of repeat dose therapy of AXER-204 compared to placebo on function and activities of daily living (ADL) measures as assessed by:
 - Primary Efficacy Objective:
 - International Standards for Neurological Classification of SCI (ISNCSCI) Upper Extremity Motor Score (UEMS)
 - Secondary Efficacy Objectives:
 - Graded Redefined Assessment of Strength, Sensation and Prehension (GRASSP) prehension performance
 - Version III of the Spinal Cord Independence Measure (SCIM III) self-care
 - Patient Global Impression of Change (PGIC) Chronic SCI

2.1.2.3 Exploratory Objectives

- To evaluate the efficacy of repeat dose therapy of AXER-204 compared to placebo as assessed by the following:
 - ISNCSCI UEMS for the side with the higher baseline score and the side with the lower baseline score
 - ISNCSCI total motor and sensory scores
 - GRASSP strength, sensation and prehension ability scores
 - SCIM III mobility scores
 - International Standards to document remaining Autonomic Function after Spinal Cord Injury (ISAFSCI)
 - Patient Reported Outcomes
 - CUE-Questionnaire (CUE-Q). Assesses subject-reported upper limb function.

- SF-36 v2. Provides a patient-reported Quality of Life (QoL) assessment. SF-36 will provide data on the subjects' perceived health and well-being over the course of the study.
- Neuro-QOL Item Bank v1.0 Upper Extremity Function (Fine Motor, ADL)
- Clinical Global Impression of Change (CGIC) from GRASSP Prehension Performance Video Recordings
- Modified Ashworth Scale (MAS) for spasticity.
- Brief Pain Inventory (BPI) mean Pain score and mean activity interference score
- Exploratory biomarkers of target engagement and axonal growth may be assessed.

2.2 Overall Study Design

Study RNX-AX204-101 is a two-part study that will be run sequentially. Each Part will be conducted at approximately 5 centers in the United States.

For each Part, eligible subjects will be between the ages of 18 to 65 years inclusive, male or female, with a traumatic spinal cord injury that occurred at least 1 year prior to the screening date, and with significant neurologic impairment of the hands and arms. Subjects who participated in Part 1 may be evaluated for enrollment in Part 2 provided at least 6 months will have elapsed between the dose received in Part 1 and the initiation of dosing in Part 2.

The study will be analyzed separately for Part 1 and Part 2 as illustrated in Figure 1. All Part 1 outputs will be created when Part 1 is finished and database for Part 1 is locked. For Part 2, when all enrolled patients have completed the 6-month visit, data will be cleaned and locked and then unblinded to be analyzed for the primary and secondary efficacy endpoints to compare treatment effects from baseline to Study Day 169. Although the data will be unblinded for and ReNetX staff, the raters, patients and primary investigators will remain blinded until final database lock following Study Day 253. All safety summaries will also be created. When all patients have completed Study Day 253 visits, the database will be locked and all outputs including analysis for treatment effect on study day 253 will be created including all data points from start of the Part 2 to end of study for patients enrolled in Part 2.

Figure 1 Sequence of Data Analyses

2.2.1 Part 1

Part 1 is a multicenter, open-label, single ascending dose study in subjects with CSCI. Four cohorts of 6 subjects each are planned, with subjects within each cohort expected to receive the same dose of AXER-204. Up to 24 subjects will be enrolled in Part 1. If the Maximum Tolerated Dose (MTD) is reached prior to the fourth cohort, the sponsor may enroll the remaining subjects (up to a total enrollment of 24 for the study) to obtain further data at the tolerated dose levels. The sponsor in conjunction with the investigators and medical monitor will determine dose escalation.

The starting dose is 3 mg. Dose escalation will proceed to 30 mg, 90 mg, 200 mg contingent on safety and tolerability. Dosing volumes will be given as follows:

- Cohort 1: 3 mg, 10 mL
- Cohort 2: 30 mg, 10 mL
- Cohort 3: 90 mg, 9 mL
- Cohort 4: 200 mg, 20 mL

Study participation for each subject in Part 1 is expected to be up to 16 weeks in duration, with up to an 84-day screening period, a 3-day in-clinic treatment period, and a follow-up period through 29 days post-dose:

 Screening (up to 84 days prior to Study Day 1). Subjects have 84 days from the time of signing informed consent to complete their screening assessments and, if needed, their washout period for prohibited concomitant medications. However, clinical laboratory tests required for screening must be completed within 28 days prior to Study Day 1.

- Treatment period: Check-in Day 1, administration of study drug, 3-night inclinic stay, and discharge on Day 4 following the completion of all scheduled procedures.
- Follow-up: Subjects will have follow-up visits for up to 29 days post-dose as follows: subjects will receive a phone call on Study Days 5, 6 and 7 to inquire about their general health and will return to the clinic for visits on Study Day 8 (± 1 day), Study Day 15 (±3 days) and Study Day 29 or Early Termination (ET) (± 4 days).

2.2.2 Part 2

Part 2 is a multicenter, randomized, double-blind, placebo-controlled, repeat dose study in CSCI subjects. Approximately 32 subjects will be randomized (ratio 1:1) to receive AXER-204 or placebo (an isotonic phosphate buffered saline formulation). Subject to review of the safety, tolerability, and pharmacokinetic data from Part 1 and DSMB approval, the dose will be 200 mg given once every 3 weeks for 15 weeks as outlined in the schedule of events. Subject to DSMB approval, the dose may be reduced to 90 mg and the dose interval may be modified based on data from Part 1 but is not expected to be less than once every 14 days or more than 28 days. Subject to DSMB approval, the dose and dose frequency may also be adjusted during Part 2 based on emergent safety and tolerability data.

Study participation for each subject in Part 2 is expected to be up to 337 days in duration, with up to an 84-day screening period, a 104-day treatment period, and then post treatment follow-ups at Study Days 137, 169, and 253:

- Screening (within 84 days prior to Day 1). Subjects have 84 days from the time of signing informed consent to complete their screening assessments and, if needed, their washout period for prohibited concomitant medications. The screening laboratory tests must be completed within 28 days prior to Study Day 1.
- Treatment Period (15 weeks). Investigational product given approximately every 21 days for up to 104 days per subject. A telephone call to assess status regarding any adverse events will be conducted on Study Day 8 (±3 days).
 - Eligible subjects will be randomized to either AXER-204 or to placebo. The randomization will be stratified based on pre-treatment American Spinal Injury Association Impairment Scale (AIS) grade (AIS A,B vs. AIS C,D) and prior receipt of study drug in Part 1 (Received AXER-204 in Part 1 vs. Did not receive AXER-204 in Part 1). The pre-treatment AIS grade is determined on Visit 2, Day 1.

 Follow-up (21 weeks). Following the last Treatment Period dose of investigational product or Early Termination of dosing, a telephone call to assess status regarding any adverse events will be conducted on Study Day 137 (± 7 days) and two follow-up visits will occur at Study Days 169 (± 7 days) and 253 (± 7 days).

2.3 Sample Size

2.3.1 Part 1

The Part 1 sample size of 24 (6 subjects per dose) was derived empirically from experience with previous single ascending dose clinical studies in other disorders and is deemed appropriate to achieve the study objectives, with adequate exposure to assess safety for dose selection in Part 2.

2.3.2 Part 2

The Part 2 sample size of approximately 32 subjects was selected with the goal of ensuring adequate power for detecting meaningful treatment-related change in bilateral Upper Extremity Motor Score, UEMS (Score from 0 to 50). Little or no spontaneous improvement in motor score is expected in people with chronic SCI, more than one year from injury (i.e. $\Delta UEMS = 0$) (Fawcett et al. 2007). As shown in Table 1, we have targeted detection of 5-point improvement in UEMS (and possibly less) as functionally relevant in the chronic cervical SCI patients recruited to this study. The potential impact of missing data and a correction for non-normal distribution of the data are not included in these estimates.

Table 1	Estimated power as a function of enrollment, effect size, and
normal v	riability of the outcome measure (Δ UEMS)

	∆ UEMS = 5		∆ UEMS = 4		∆ UEMS = 3	
Enrollment	nt SD = 3 SD = 4		SD = 3	SD = 4	SD = 3	SD = 4
32	99%	96%	95%	78%	78%	53%
26	98%	92%	90%	68%	68%	45%
20	94%	85%	80%	56%	56%	35%

SD = Standard deviation of the change in UEMS

Based on 2 sided α = 0.05 using NQuery (Version 4.0).

 Δ UEMS: A smaller improvement in Δ UEMS (e.g. 2 points) could be clinically meaningful if it occurred in a muscle group essential for a particular activity of daily living such as grasping in the chronic SCI population. A 3-point improvement in

CONFIDENTIAL

Statistical Analysis Plan ReNetX Bio, Inc

UEMS has been identified as the minimum clinically important difference in acute cervical SCI patients (Scivoletto et al. 2013). Although a minimum clinically important difference in UEMS has not been determined for chronic SCI patients, chronic SCI patients may have greater awareness of personal benefit resulting from changes due to their stable baseline function (Wu et al. 2015).

Standard Deviation (SD): Although we estimated SD of 3 and 4, the data from the 23 patients evaluated at screening and Day 29 in Part 1 of this trial yielded a SD for \triangle UEMS of 2.0 which may be more representative of variability in our patient population and the rater consistency attained in the trial that may provide us with even higher power.

3. Efficacy and Safety Variables

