## 15. STATISTICS

## 15.1. Sample Size

The Part 1 sample size was derived empirically from experience with previous single ascending dose clinical studies in other disorders and is deemed appropriate to achieve the study objectives.

The Part 2 sample size was selected to ensure adequate power for detecting treatment-related change in bilateral UEMS (Score from 0 to 50).

A 5-point difference, between the treated and placebo groups, in the change from baseline to 6 months in bilateral UEMS is considered clinically meaningful. Analysis of historical data for cervical SCI patients for the period between ~6-12 months following acute SCI indicates a standard deviation of bilateral UEMS change over 6 months to be around 3 to 4 points.

With a sample size of 12 subjects per active and placebo group, Part 2 of the study has 80% power with Type I error of  $\alpha$ =0.05 (two sided), assuming a 5-point difference as indicated above, and with a common standard deviation within each treatment group of approximately 4 in the change from baseline to 6 months in bilateral UEMS.

Accounting for uncertainties in the assumptions based upon historical data used to extrapolate for estimating the sample size in this study and the need for estimation of missing data a sample size of approximately 16 subjects per treatment arm (32 total) will be randomized.

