8.1 General Principles

- All data processing, summarization and analyses will be performed using SAS Environment / Version 9.4 (or later) of the SAS[®] statistical software package.
- The following principles will be applied to all TFLs unless otherwise stated:

Table 6 Statistical Analysis General Principles

Principle	Value
Significant tests	Two sided and use a 5% significance level
Treatment group labels and order	Part 1: AXER-204 xx mg
presented	Part 2: AXER-204 200 mg; Placebo
Tables	Data in summary tables presented by dose
	cohort/treatment group, assessment (where
	applicable), and visit (where applicable).

Principle	Value
Listings	All data collected presented by dose
	conort/treatment group, subject, and visit (where applicable) unless otherwise specified
Descriptive summary statistics for	Number of subjects (N), mean, standard deviation
continuous variables	(SD), median, minimum, maximum.
Descriptive summary statistics for categorical variables	Frequency counts and percentages [n (%)]
Denominator for percentages	Number of subjects in the analysis population, unless otherwise specified.
Include "Missing" as category	Yes, when the number missing is greater than zero for at least one dose cohort/treatment group.
Display for percentage	One decimal place, except for 100%
Display for 0 percentages	0
Display to one more decimal place than collected value	Mean, Median, Mean Difference
Display to two more decimal places than collected value	Standard Deviation
Limit of precision for displays	3 decimal places
Date Format	DDMMMYYYY
TFL orientation	Landscape
TFL output	For all tables and listings, 2.54 cm for the
	top/bottom/left/right margins and 8-point Courier New font

• For both safety and efficacy analysis, the baseline value will be defined as the last non-missing value before the first dose of study treatment.

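### SAP Table 1 overstates power for a 5-point difference with SD 4: it prints 96/92/85%, while its stated two-sided 5% level gives 92.8/86.4/75.3%

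*SAP*

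**What the plan says.** SAP section 2.3.2 tabulates power for total enrollments of 32, 26 and 20, for differences of 5, 4 and 3 points in the change in bilateral UEMS, each with SD 3 and SD 4. A single footnote covers all 18 cells: "Based on 2 sided α = 0.05 using NQuery (Version 4.0". No other significance level or test is given for any column. SAP section 8.1 sets the same convention for significance tests: "Two sided and use a 5% significance level".

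The column for a difference of 5 with SD 4 reads 96%, 92% and 85%. The next column, a difference of 4 with SD 3, reads 95%, 90% and 80%. The two lower rows are printed as "26 98% 92% 90% 68% 68% 45" and "20 94% 85% 80% 56% 56% 35" (percent), in the order 5/3, 5/4, 4/3, 4/4, 3/3, 3/4 (difference/SD).

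The text before the table adds a caveat: "The potential impact of missing data and a correction for non-normal distribution of the data are not included in these estimates".

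Protocol section 15.1 sizes Part 2 on the same scenario, a 5-point difference with SD about 4 at two-sided 5%: "With a sample size of 12 subjects per active and placebo group, Part 2 of the study has 80% power".

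**The concern.** For a two-arm comparison of means at fixed enrollment and significance level, power depends on the difference and the SD only through their ratio, and it rises with that ratio. A ratio of 1.25 (5/4) must therefore have less power than 1.33 (4/3). Table 1 shows the reverse in all three rows: 96 against 95, 92 against 90, 85 against 80. No test, significance level or rounding rule applied to the whole table can produce that order. The table respects the principle elsewhere, since its two columns with ratio 1.00 (4/4 and 3/3) are identical at 78/68/56.

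The column also disagrees with the protocol. The SAP prints 85% with 10 per arm, while protocol section 15.1 states 80% with 12 per arm for the same difference, SD and significance level.

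At stake is the SAP's record of power for the planning scenario. The rows for 26 and 20 show how much power survives with fewer subjects, and they do so before any allowance for missing data. Too high a figure there makes the trial look more tolerant of lost subjects than it is. SAP section 10 reports a primary comparison that did not reach significance, so readers may turn to this table to judge what the trial could have detected.

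**Working it through.** **Inputs.** Two-sided significance level 0.05 (Table 1 footnote; SAP section 8.1). Allocation 1:1 (SAP section 2.2.2), so n = 16, 13 and 10 per arm for totals of 32, 26 and 20. Differences Δ of 5, 4 and 3 points with SD 3 or 4 (Table 1). No allowance for missing data or non-normality (text before Table 1). The footnote does not name the test, so a two-sample equal-variance t-test was tried first.

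**Formula.** Degrees of freedom df = 2n − 2; noncentrality λ = (Δ/SD)·√(n/2); critical value c = the 97.5th percentile of t on df. Power = P(T > c) + P(T < −c), where T is noncentral t with df and λ.

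**Step 1: reproduce the table.** Power in percent, with the printed value in brackets:

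| Δ / SD | Ratio | N = 32 | N = 26 | N = 20 |
|---|---|---|---|---|
| 5 / 3 | 1.67 | 99.53 (99) | 98.27 (98) | 94.08 (94) |
| **5 / 4** | **1.25** | **92.79 (96)** | **86.37 (92)** | **75.29 (85)** |
| 4 / 3 | 1.33 | 95.43 (95) | 90.33 (90) | 80.49 (80) |
| 4 / 4 | 1.00 | 78.14 (78) | 68.67 (68) | 56.20 (56) |
| 3 / 3 | 1.00 | 78.14 (78) | 68.67 (68) | 56.20 (56) |
| 3 / 4 | 0.75 | 53.72 (53) | 45.06 (45) | 35.51 (35) |

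Fifteen cells match exactly when truncated. Truncation, not rounding, is the table's convention: 68.67 is printed as 68 and 53.72 as 53. The three cells for 5/4 do not match.

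**Step 2: the disputed column in detail.**

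- N = 32: df = 30, λ = 1.25 × √8 = 3.536, c = 2.042, power 92.79%.
- N = 26: df = 24, λ = 1.25 × √6.5 = 3.187, c = 2.064, power 86.37%.
- N = 20: df = 18, λ = 1.25 × √5 = 2.795, c = 2.101, power 75.29%.

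The overstatement is 96 − 92.8 = 3.2, 92 − 86.4 = 5.6 and 85 − 75.3 = 9.7 points. The chance of missing a true 5-point difference is 7.2%, 13.6% and 24.7%, where the printed column implies 4%, 8% and 15%.

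**Step 3: alternative explanations.**

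- *Normal approximation, two-sided.* It gives 94.2/89.0/79.8% for this column, still below the printed values, and it breaks other columns (80.7% where 78% is printed for 4/4 at N = 32).
- *A mistyped SD.* With Δ = 5, matching 96/92/85% would need SD 3.69, 3.63 and 3.53 in the three rows. No single SD fits.
- *A one-sided 5% test (equivalently two-sided 10%).* For 5/4 this gives 96.48/92.65/85.15%, which truncates to the printed 96/92/85. It does not fit the rest of the table (for example 97.9% for 4/3 at N = 32, printed 95). One column run one-sided is therefore a likely cause, but the documents do not confirm it.

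**Step 4: cross-check with the protocol.** At 12 per arm: df = 22, λ = 1.25 × √6 = 3.062, c = 2.074, power 83.29%. The protocol's 80% is slightly conservative. At 11 per arm power is 79.63%, so 24 is the smallest balanced total with at least 80%. A total of 20 cannot reach 85%.

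**The case against.** The arithmetic is hard to contest; the case on the other side is that it hardly matters. In the row for the planned enrollment the error is 3 points and power stays well above 90%. No analysis uses Table 1. No section plans for 20 subjects, and protocol sections 7.2 and 9.1 allow replacement of subjects who discontinue if power is threatened. This SAP is dated 5 August 2022, and its section 10 was written after the Day 169 unblinding, so the correction can no longer influence sizing. The SAP also reports an SD of 2.0 from Part 1; at that SD power for a 5-point difference exceeds 99.9% in all three rows. Finally, the test is not named, and the primary analysis is a covariate-adjusted MMRM, so the table is only a planning approximation.

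Most of this limits the consequence and is accepted: the correction is to the record, not to the design. It does not rescue the column. The Part 1 SD covers screening to Day 29, not six months, and cannot validate cells labelled SD 4. The choice of test is settled by the 15 matching cells, and the ordering contradiction does not depend on it. Other columns already show power below 80% without comment, so the proposed note on N = 20 is less essential than the cells themselves. It is still useful, because this is the one scenario where the printed figure lies above 80% and the recomputed one below it.

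**Conclusion.** The concern holds. The column for a 5-point difference with SD 4 does not follow from the table's stated basis and is inconsistent with the column beside it. The values should be 92.8%, 86.4% and 75.3% in place of 96%, 92% and 85%. The exact figures assume an equal-variance two-sample t-test with equal arms, which the rest of the table bears out. That the column is wrong needs no such assumption.

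The planned enrollment of 32 keeps about 93% power in this scenario, so sample size, design and analyses stand. What changes is the apparent margin: at 20 subjects the trial would have had about a one-in-four chance of missing a true 5-point difference, not 15%, before any allowance for missing data or non-normality.

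**What to change.** In SAP Table 1, replace the three cells for a difference of 5 with SD 4 by 92%, 86% and 75%, which keeps the truncation used in the other 15 cells, or by 93%, 86% and 75% if rounding is preferred. Name the test in the footnote (two-sample t-test, equal arms). Add one sentence saying that power at an enrollment of 20 is below 80% in this scenario, before any allowance for missing data or non-normality. Leave protocol section 15.1 as it is.

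The cost is three cells, a few words in the footnote and one sentence. Enrollment, design and analyses do not change.
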